5.5 Premature Termination, Suspension, or Extension of Study

It is agreed that either the investigator and/or APT may terminate this study at any time, provided written notice is submitted at a reasonable time in advance of intended termination. The study may be extended to obtain expanded efficacy and safety information as per the adaptive trial design and/or to obtain long-term safety information. Also, a decision on the part of the IRB/EC to suspend or discontinue testing, evaluation, or development of the product may lead to discontinuation/termination of a study subject's participation.

A study conducted at a single study site in a multicenter study may also warrant termination under the following conditions:

- Failure of the Investigator to enroll patients into the study at an acceptable rate
- Failure of the Investigator to comply with pertinent regulations of appropriate regulatory authorities
- Insufficient adherence to protocol requirements
- Submission of knowingly false information from the research facility to the sponsor, study monitor, or appropriate regulatory authority

6. Study Agent/Product

6.1 Device

The Tango Belt (the "Device") is a wearable belt designed to enable safer mobility of geriatric individuals (≥ 65 years of age) at risk for fall injury by mitigating major hip injuries due to falls. The Tango Belt is a patient-contacting electronic device made out of medical grade plastics and biocompatible fabrics. It is worn around the waist at the iliac crest, secured by a buckle. It comes in 5 sizes, XS, S, M, L, and XL, to accommodate wearers with a waist circumference between 29-50 inches (covering the 5th-95th percentile of older adults in the US); each belt is further adjustable to prevent sliding past the hips or elevating out of position.

The Tango Belt contains a fall-in-progress detection algorithm which can detect a serious hip-impacting fall-in-progress using built-in sensors and deploy an automotive-grade cold-gas airbag to protect the hips from ground impact forces. When connected to Wi-Fi, the Tango Belt can send automated fall and impact alerts to caregivers and Healthcare Providers (HCPs) while recording motion and event data, which can then be analyzed for usage-based metrics viewable via a companion mobile app and/or desktop app. The Tango Belt can also send manually activated alerts for help, triggered by pressing a button on the belt buckle, when connected to Wi-Fi. Alerts are sent in the form of SMS texts and emails to alert recipients designated in the mobile or desktop Companion App. The Tango Belt can also detect non-serious hip-impacting or non-hip impacting falls in which the wearer may have incurred a minor injury (i.e., not a major hip injury) and/or may be unable to get up.

Additionally, the belt can be periodically surface disinfected using a germicidal wipe. Further, the belt contains a non-replaceable lithium-ion battery, which requires recharging via the included specially designed AC adapter every several days depending on wear duration. An optional Safety Latch can be installed by care staff on any belt to prevent inadvertent unbuckling. Lastly, if airbag deployment occurs, the Tango Belt cannot be reused.

The Tango Belt's Companion App (available in mobile and desktop versions) enables the following added functionality: 1) connecting the belt to Wi-Fi (mobile version only), 2) inputting contact information for alert recipients, 3) viewing dashboard metrics (e.g. Compliance and Daily Wear), 4) taking or administering the FES-I survey, and 5) managing a fleet of multiple belts within a facility setting.

6.2 Acquisition

The sponsor will provide the Tango Belts in numbers allocated to the sizes appropriate for enrolled subjects in the intervention group. The Tango Belts will be delivered to the clinical sites with chargers, instructional materials, and cleaning materials during the time of EMR screening in preparation for enrollment. Extra Tango Belts will be provided

to all clinical sites in sizes allocated for replacement in the case of device malfunction or airbag deployment.

6.3 Appearance and Labeling

The main component of the Tango Belt is the belt itself, which is shipped and stored in a custom foam-padded cardboard box also containing the Tango Belt Product Guide and Tango Belt charger. Each Tango Belt, including its individual box, is clearly labeled with its size and unique Serial Number (aka "ID number"), which is number located on the inside of the right zipper pouch and is uniquely tied to its lot manufacturing record and any digital data stored in the APT cloud. Physical labeling on the belt also includes graphical symbols to aid proper donning, warnings, and contact information. Further, the Product Guide includes instructions for use, warnings, cautions, and useful tips for operation. The Support page of the Tango Belt website also includes instructional videos covering the operation of the belt and companion app, as well as useful tips and cautions.

6.4 Product Storage and Stability

Tango Belt is designed to be shelf-stable for at least 12 months, in package, in climate-controlled storage. The Tango Belt should not be exposed to temperatures outside the range of -4° to 122° F (-20° to 50° C). If stored unused for a long period of time the belt should be recharged prior to use. For purposes of this clinical trial, no other special storage instructions apply. Product usage life of the Tango Belt is 3 years from the date of first use.

6.5 Preparation

The Tango Belt must be properly sized to the waist of each intervention subject. Determination of proper belt size and further adjustment of the built-in sizing strap is described in the Product Guide and online training videos. Prior to use, the Tango Belt should be charged using the included charger; charging time requires approximately 3 hours when the battery is fully depleted.

Additionally, the Tango Belt Companion App (running on a compatible mobile device) must be used to complete the following preparation steps prior to first use:

Each belt must be connected to the site's Wi-Fi network using the Guided Setup

- A new "Wearer" should be created for each intervention and given a wearer name consistent with the subject naming scheme for the study
- Lastly, the sized belt should be ASSIGNED to the newly created Wearer via its unique Serial Number located on the belt and package labeling

Upon completion of the steps above, the Tango Belt can then be provided to the intervention subject to begin their 6-month study participation (subject to successful completion of their 14-day run-in period).

6.6 Device accountability procedures

An electronic data capture (EDC) platform will be custom-developed for this study and utilized by investigators or designees at each site for the purposes of electronically collecting and managing CRF data throughout the study. For each intervention subject, the investigator or designee will enter into the EDC platform the Tango Belt ID number along with a unique subject identifier obtained from APT to enable matching of EDC data with data stored in APT's cloud.

Labels will be provided for marking room numbers on the external aspect of the Tango Belt for easy identification of subject assigned device.

Inventory tracker sheets will be provided for quick reference of care team members and study investigators on-site for device allocation.

Lastly, metal rolling carts will be provided to each site to allow for secure storage and charging of belts provided for this study.

7. Study Procedures and Schedule

7.1 Investigator Training

All investigators involved in the clinical study will attend to the following training:

- Good Clinical Practices (GCP) and Research Ethics Training by an approved provider. Attendance certificates will be held at the clinical study sites
- Electronic Documentation System for recording of all data required on the CRF per this protocol
- Use and care of the Tango Belt
- Use of the Tango Belt mobile and desktop apps as appropriate

7.2 Evaluations and Scheduled Data Collection Flow Chart

Evaluation	Visit 1 Screening/ Baseline Visit (+/- 14 days)	Visit 2 14-day Run-In (+/- 2 days)	Visit 3 90-Days (+/- 10 days)	End of Study 180-days (+/- 30 days)	Unscheduled Visit /
Render Informed Consent	Х				
Demographic information	Х				
Medical / Fall history	х				
BIMS	Х				
Fall mitigation plan of care	Х		Х	Х	Х
FES-I (short version)	x		Х	Х	Х
Inclusion/Exclusion criteria review	Х		Х	Х	Х
Tango Belt adherence		Х	Х	X	Х
Adverse Events (including Fall event information)			Х	Х	Х
Device deficiencies			Х	Х	Х

7.3 Study Visit Descriptions

Visit 1 Baseline:

• Informed Consent will include the provision of the Informed Consent Form (ICF) with overview of the clinical study proposed and informational materials that may include: video description, flyer and discussion of the Tango Belt technology. Informed consent will be obtained in person by qualified clinical study site personnel delegated to this task by the site investigator and before any study related procedures and/or assessments can be performed. If the subject has a legally authorized representative (LAR) documented as a person of authority (POA), that person identified in the EMR will be contacted with the same information and presented with the ICF. If there is telephonic agreement of study consent, this will be noted by the CRA on the ICF with date, time and indication of LAR, with tow (2)

copies sent via email or USPS to the LAR for final signature. An email including the ICF with explanation of the clinical study and inclusion of the noted information can also be shared with a LAR for electronic signature for subject informed consent. Contact information for the clinical site study investigator will be provided to the subject/LAR to offer communication in regard to any questions or concerns for consenting to participation in the clinical study. The subject will be provided the Short version of the FES-I if they have the cognitive capability to do so. BIMS score of 13-15 indicates ability to take the Short version of the FES-I.

- The subject will be assigned a Tango Belt of the correct size based on measuring their waist size and the belt will be introduced to the subject with specific fitting applied using the sizing strap for best comfort. The Tango Belt assignment will be performed using the Tango Belt Companion App to allow for data tracking for this subject. An order for wearing of the Tango Belt will be applied to the medical chart and the care team will be notified of the patient's inclusion in the study with attention for wear adherence and charging cycle.
- The baseline metrics of medical and fall history, fall mitigation plan, and mobility level will be taken directly from the MDS and/or EMR within the electronic documentation system utilized at the clinical study site.

Visit 2 Run-in period (14 days +/- 2):

 Metrics of the compliance to wear of the Tango Belt by the subject defined as at minimum 64% (at least 1 hour a day for 9 days out of 14) will be provided by sponsor to the CRA. If the subject is not utilizing the device for at least the minimum amount of time, they will be determined to be a screen failure and withdrawn.

Visit 3 Midterm (90 days +/- 10):

- Metrics of changes in fall mitigation plan, mobility level and fall events including falls, falls with major injury, adverse events (whether not pertaining to the Tango Belt), emergency department visits, and hospital admissions will be taken by the site investigator or designee research assistant directly from the MDS and/or EMR within the electronic documentation system utilized at the clinical study site.
- Metrics of Tango belt wear days and wear hours/day will be provided to the site investigator or designee research assistant from the sponsor or obtained from the Tango Belt Companion App.
- Metrics of device deficiencies, device discrimination between types of falls, airbag deployments, and alerting will be provided to the site investigator or designee research assistant by sponsor from the Tango Belt cloud.

End of Study (180 days +/- 30):

 Metrics of changes in fall mitigation plan, mobility level and fall events including falls, falls with major injury, adverse events (whether or not pertaining to the Tango Belt), emergency department visits, and hospital admissions will be taken by the site -

- investigator or designee research assistant directly from the MDS and/or EMR within the electronic documentation system utilized at the clinical study site.
- Metrics of Tango belt wear days and wear hours/day will be provided to the site investigator or designee research assistant by sponsor or obtained from the Tango Belt Companion App.
- Metrics of device deficiencies, device discrimination between types of falls, airbag deployments, and alerting will be provided to the site investigator or designee research assistant by sponsor from the Tango Belt cloud.
- Tango Belt will be collected by the sponsor for return to Active Protective Technologies, Inc.

Unscheduled Visit (AE, hospitalization, change in status in medical care plan):

- Metrics of changes in fall mitigation plan, mobility level and fall events including falls, falls with major injury, adverse events (whether or not pertaining to the Tango Belt), emergency department visits, and hospital admissions will be taken by the site investigator or designee research assistant directly from the MDS and/or EMR within the electronic documentation system utilized at the clinical study site.
- Metrics of Tango belt wear days and wear hours/day will be provided to the site investigator or designee by sponsor or obtained from the Tango Belt Companion App.
- Metrics of device deficiencies, device discrimination between types of falls, airbag deployments, and alerting will be provided to the site Investigator or designee research assistant by sponsor from the Tango Belt cloud

Major Hip Injury Adjudication: for 90-day and 180-day adverse event reporting of Fall with Major Injury:

In the event of an identified Fall with Major Injury, the determination of Fall with Major
Hip Injury will be independently assessed by a qualified medical expert in the field of
geriatric medicine after receiving blinded data regarding the injury.

8. Assessment of Safety

8.1 Definition of Adverse Event (AE)

An Adverse Event (AE) is defined as:

Any untoward medical occurrences in a patient or subject receiving an investigational medical device and does not necessarily have to have a causal relationship with the device under investigation. An AE can therefore be any unfavorable and unintended sign (including abnormal laboratory finding), symptom, or disease temporally associated with the use of a medical device whether or not considered related to the medical

device. Any fall event is considered an AE for this study.

8.2 Definition of Serious Adverse Event (SAE)

A Serious Adverse Event (SAE) is defined as:

An AE that results in any of the following outcomes:

- Results in death;
- Is life-threatening;
- Requires in-patient hospitalization or prolongation of existing hospitalization;
- Results in persistent or significant disability/incapacity

8.3 Classification of AE

i. Severity of event

Each AE must be described as follows:

- the date of onset;
- date of resolution;
- severity;
- frequency of the event (single episode, intermittent, continuous);
- action taken (none, medical and/or surgical);
- relationship to study device;
- seriousness criteria must be recorded.

Each adverse event must be recorded separately.

AE Severity will be assessed using the following definitions:

Mild Aware of sign or symptom, but easily tolerated

Moderate Discomfort enough to cause interference with usual activity

Severe Incapacitating with inability to work or do usual activity

ii. Relationship to Study Agent/Product

The relationship to study device will be assessed by the site investigator using the following definitions:

Not Related Evidence exists that the adverse event definitely has a cause

other than the study device (e.g., pre-existing condition or underlying disease, intercurrent illness, or concomitant medication) and does not meet any other criteria listed.

Possibly Related

A temporal relationship exists between the event onset and administration of study device. Although the adverse event may appear unlikely to be related to the study device, it cannot be ruled out with certainty, and/or the event cannot be readily explained by the patient's clinical state or concomitant therapies.

Probably Related

A temporal relationship exists between the event onset and administration of study device and appears with some degree of certainty to be related based on known mechanism of action of the device. It cannot be readily explained by the patient's clinical state or concomitant therapies.

Definitely Related Strong evidence exists that the study device caused the adverse event. There is a temporal relationship between the event onset and administration of the study device. There is strong mechanistic evidence that the event was caused by the study device. The patient's clinical state and concomitant therapies have been ruled out as a cause.

Adverse events related to the Tango Belt could include the following:

- Discomfort, soreness, or injury due to normal wear of the belt, particularly in subjects who are very frail and thin and/or when the belt is not properly sized or fitted to the subject
- Discomfort, soreness, or injury caused by airbag deployment

iii. Adverse Event Reporting Procedures

Apparent Device malfunctions can be troubleshooted by site staff following provided materials, or by contacting sponsor for support, and should be recorded in patient files, along with initial date of occurrence, brief description, did it cause adverse events, whether damage is apparent. Malfunctions that impact essential performance, as defined in the Instructions for Use, should be recorded immediately and reported immediately to site-investigator. The site investigator may seek additional support from sponsor, but records in the EDC when a device is replaced due to malfunction, with date of replacement and start of malfunction. A device that doesn't maintain essential performance, as defined in the Instructions for Use, should be replaced (e.g. fails to power on, deploys without a fall, solid red light, blinking blue light). The site shall coordinate with the Sponsor Monitor for return and replacement, as needed.

All adverse events are to be evaluated for severity, relationship to product and whether they constitute an SAE, recorded in the EDC, to be reviewed by PI as described in section 8.4. PI continually monitors the enrolled study subjects for AEs and possible SAEs in the medical record.

PI should be notified immediately upon, Serious Adverse Event, fall event, or an AE that impacts utilization of the device.

Serious Adverse Events (SAE's) including status changes indicated in study subject medical records receive immediate attention of the Principal Investigator (PI) for consideration of device-related SAE. Serious AE (SAE) are to be reported to Sponsor and the IRB within 24 hours of the site becoming aware of the event. SAE notifications to the Sponsor are to be reported and completed via EDC.

Upon a fall event, site investigator is to initiate a Fall report, to gather evidence needed for the eventual adjudication of the Adverse Event, if required. Falls with Major Injury will be reviewed by the medical expert adjudicator as outlined in section 7.3. (Note, a Fall with Major Injury could *also* be considered a SAE for purposes of IRB reporting).

8.4 Safety Oversight

This trial is not conducted in an emergency setting and informed consent is being collected, so a Data Monitoring Committee is not required under regulation. The device poses non-significant risk and has been observed in a real-world setting (see section 2.3).

The Medical Monitor and Principal Investigator will oversee the safety of the study including any AEs and SAEs reported by the clinical Investigative Sites. Notification of any AEs will be obtained by the Principal Investigator via reporting from clinical site investigators in the shared CRO EDC system.

Adverse Events (AEs) that occur will be captured in the 90-day and 180-day visit reporting in the EDC for PI review.

9. Clinical Monitoring Procedures

Monitoring will be conducted by Sponsor and/or designee to ensure investigator and site personnel are in compliance with:

- The signed Clinical Trial Agreement,
- This Study Protocol,
- Adherence to applicable FDA regulations,
- Any conditions of approval imposed by the IRB or FDA,
- Ensuring the rights and well-being of the subjects are protected,
- Ensuring the reported study data are accurate, complete, and verifiable from source documents, and
- Ensuring the conduct of the study is in compliance with Good Clinical Practice.

Subject CRFs will be electronically completed and reviewed for completeness and accuracy as well as for any evidence suggesting subject risk. Risk can be anything that can affect subject safety and can be many factors including but not limited to: the reporting of false or inaccurate data, study visits and/or study procedures not being performed as required per protocol, misconduct or non-compliance by subject and/or site staff, and anything that can potentially harm or cause discomfort to the subject. Where any discrepancies are noted, they will be resolved with the investigator and/or an individual designated by the investigator. When the data are incomplete, attempts will be made to obtain the missing data.

Monitoring procedures and frequency will be conducted throughout the course of this study according to the Clinical Monitoring Plan. Monitoring visits will focus on the status of regulatory documents, adherence to the protocol, review of informed consents, adverse event reporting, device accountability, and a comparison of source documentation against electronic case report forms (eCRFs). Qualified site study personnel are expected to spend some time with the clinical monitor to resolve queries and review action items at each onsite monitoring visit.

The investigator(s)/institution(s) will permit trial-related monitoring, audits, IRB review, and regulatory inspection(s), providing direct access to source data/documents.

Representatives of the sponsor may request access to all study records, including source documents, for inspection and copying during normal business hours.

10. Statistical Considerations

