Upon preliminary enrollment, utilization of the Tango Belt will be prescribed by the site's physician and written into the subjects' plan of care at the care residence. A Tango Belt of appropriate size based upon waist measurement will be provided to the subject by the investigator or designee. The subject will be assigned to the Tango Belt ID located in the APT cloud electronically via Tango Belt companion app for data tracking. The Tango Belt size will be adjusted for most comfortable and appropriate fit using the sizing strap located in the left side zipper pocket of the Tango Belt. The Tango Belt will be prescribed to be worn up to 24 hours/ day with removal for bathing activities, dressing as needed, twice a week at minimum for charging and upon subject request. Baseline metrics will be obtained from the subjects' EMR. The enrolled participant will be

assessed for cognition level via the BIMS if this has not already been taken as part of the EMR. Assessment of balance confidence using the short version of the FES-I if they are cognitively capable of completing the survey with a BIMS Score of 13-15. (Appendix 2 – Study Questionnaire)

Enrolled subjects in the intervention group will then proceed through a run-in period of 14 days to assess adherence to utilization of the Tango Belt. At 14 days, if the subject is demonstrating adherence to use of the device of at least 64% as viewed by the investigator or designee in the Tango Belt companion app dashboard as "Compliance" (defined as wearing the device for at least 1 hour per day for at least 9 of 14 days), they will be fully enrolled into the study and proceed through the study duration. Subjects who do not meet the run-in period requirement will be withdrawn from the study.

Screen Failures in this study would include study candidates that:

- Do not meet inclusion criteria
- Meet any exclusion criteria
- Do not fit within the range of Tango Belt sizing available
- Do not comply with the minimum device utilization of 64% within the run-in period

To account for the relatively high morbidity and mortality of the target study population, we will assume a 20% in-study attrition rate, and thus will aim to over-recruit by this amount beyond the target sample size statistically required for the intervention group.

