5.2.4 SAFETY POPULATION

The safety population includes all subjects who were assigned a Tango Belt and attempted the run-in period.

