8.1 ALL ADVERSE EVENTS

The occurrence of all adverse event (AEs) will be documented for all subjects from the time of enrollment. Adverse Events will be categorized into three groups based on frequency: Single episode, Intermittent, or Continuous. This categorization is in lieu of other formal coding strategies (i.e., MedDRA). The final categorization of all AE's will be performed by the Sponsor but general definitions are as follows:

- Single Episode: Any AE's that occurred only once (Fall, death, etc.) as well as the first occurrence of an AE that occurs more than once.
- Intermittent: Subsequent AE's beyond the first of each type. If a subject had more than one of
 the same AE (i.e., fall), all occurrences of that AE after the first one will be included in the
 Intermittent category.

• Continuous: Any AE's that are ongoing and not resolved. Also, any AE that the subject lives with daily but doesn't result in death.

Summaries of incidence rates of individual AEs by frequency will be prepared. Because a subject may experience more than one AE per frequency, summaries will provide both the number of subjects experiencing at least one event and the number of events. Percentages provided will be the percent of subjects experiencing one or more adverse events. In addition, incidence of AEs will be presented by severity (mild, moderate, severe) and relationship to study device.

Subjects experiencing an event within a given frequency more than once will be counted under the maximum severity/relationship experienced.

A listing of all adverse events will include the subject number, date of onset, date of resolution, severity, AE type, the severity of AE, frequency of the event, the action taken, relationship to device, seriousness, and the outcome.

An additional listing will be provided that includes both site reported and adjudicated information for AEs that are adjudicated.

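### No adverse event review is scheduled at the 14-day run-in visit, yet subjects withdrawn there stay in the safety denominator, so device-related event rates may be understated

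*Combined protocol and SAP*

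**What the plan says.** **Schedule.** In the protocol 7.2 flow chart, the row "Adverse Events (including Fall event information)" is marked at 90 days, 180 days and unscheduled visits. It is blank at baseline and at Visit 2, the 14-day run-in. The device-deficiency row has the same pattern. Protocol 7.3 gives Visit 2 a single task: "Metrics of the compliance to wear of the Tango Belt by the subject defined as at minimum 64" per cent, with figures supplied by the sponsor. Protocol 8.4 adds: "Adverse Events (AEs) that occur will be captured in the 90-day and 180-day visit reporting in the EDC for PI review".

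**Run-in failures.** Protocol 5.3 states: "Subjects who do not meet the run-in period requirement will be withdrawn from the study". Protocol 7.3 says of the same people that "they will be determined to be a screen failure and withdrawn".

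**Safety population and event window.** SAP 5.2.4 counts "all subjects who were assigned a Tango Belt and attempted the run-in period", which includes run-in failures. SAP 8.1 states: "The occurrence of all adverse event (AEs) will be documented for all subjects from the time of enrollment". It reports the percentage of subjects with at least one event.

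**Routes outside the schedule.** Protocol 8.3 iii has the PI watching the medical records of enrolled subjects on an ongoing basis. It also requires immediate notice of serious events, falls and events that affect use of the belt. An adverse event can trigger an unscheduled visit (7.3). Protocol 5.4 requires a dated reason for every screen failure or withdrawal, and CRF recording of a significant symptom or event linked to discontinuation.

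**The concern.** Safety has no primary endpoint and no data monitoring committee. It is judged from adverse event summaries alone (SAP 3.2.1, protocol 8.4).

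The subjects who lack a scheduled review are not a random subset. Protocol 8.3 ii names discomfort, soreness or injury from ordinary wear as a possible belt-related event, particularly in frail or thin subjects or where the fit is poor. Such an event can begin in the first days and lead the subject to stop wearing the belt, and too little wear is what defines run-in failure. The people most likely to have this event may therefore leave before the first scheduled occasion to ask about it, while still adding to the denominator.

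**Working it through.** The documents give no adverse event rate and no run-in failure share, so there is no stated figure to reproduce. The check has two parts.

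**1. The texts side by side**

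| Source | What it implies for a run-in failure |
|---|---|
| Protocol 7.2, 7.3 (Visit 2) | Wear is measured; adverse events and device deficiencies are not |
| Protocol 8.4 | Reporting at 90 and 180 days, which this subject does not reach |
| Protocol 5.3, 7.3 | Withdrawn at about day 14 |
| SAP 5.2.4 | Counted in the safety population |
| SAP 8.1 | Events documented from enrollment |

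The first three rows do not provide what the last two assume. SAP 8.1 does not name its population; I take it to be the Safety Population.

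The start of the window is also unclear. Protocol 5.3 treats a subject as preliminarily enrolled at consent, as enrolled during the run-in and as fully enrolled after passing it. Neither document says which of these starts the event window.

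The gap is confined to run-in failures. A subject who passes can have run-in events picked up from the record at day 90.

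**2. Possible size**

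Inputs, all assumed:
- f = share of the safety population withdrawn at run-in
- k = event risk in those withdrawn relative to those retained
- c = share of the withdrawn subjects' events still caught by the unscheduled routes
- r = event risk in those retained (it cancels)

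True rate = r × [(1 − f) + f·k]. Observed rate = r × [(1 − f) + f·k·c].

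Relative understatement = f·k·(1 − c) / (1 − f + f·k).

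Example: for f = 0.10, k = 2, c = 0, this is 0.20 / 1.10 = 18.2%. With r = 5%, the true rate is 5.5% and the table would show 4.5%. With c = 0.5 it would show 5.0%, an understatement of 9.1%.

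| k | c | f = 5% | f = 10% | f = 20% | f = 30% |
|---|---|---|---|---|---|
| 0.5 | 0 | 2.6% | 5.3% | 11.1% | 17.6% |
| 1 | 0 | 5.0% | 10.0% | 20.0% | 30.0% |
| 1 | 0.5 | 2.5% | 5.0% | 10.0% | 15.0% |
| 2 | 0 | 9.5% | 18.2% | 33.3% | 46.2% |
| 2 | 0.5 | 4.8% | 9.1% | 16.7% | 23.1% |
| 3 | 0 | 13.6% | 25.0% | 42.9% | 56% |
| any | 1 | 0% | 0% | 0% | 0% |

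The rows with c = 0 are a worst case that gives the unscheduled routes no credit. No input makes the result negative, so the bias is downward or nil.

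**The case against.** The best defence is protocol 8.3 iii. A subject who stops wearing the belt because it hurts has an event affecting use of the device, and that calls for immediate notice to the PI. The same section requires all adverse events to be entered in the EDC and has the PI following the record throughout. Protocol 5.3 calls run-in participants enrolled, so these duties can be read to cover them, and SAP 8.1 starts documentation at enrollment. Protocol 5.4 already asks for a reason for removal, and protocol 11 verifies all adverse events against source.

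Much of this stands, and it rules out two stronger readings. A reader might infer that adverse events are collected only at 90 and 180 days. The documents do not say so: 8.4 names those visits without excluding other routes, and 7.2 marks unscheduled visits as well. A reader might also infer that belt-related harm is in fact understated. That would require the other routes to miss events, which the documents do not show.

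The defence does not close the gap:
- Every one of these routes starts from an event that someone has recognised or charted. Source verification cannot find what was never written down.
- Subjects need not explain a withdrawal (5.4), and some are enrolled through a representative (5.3), so mild discomfort may go unreported.
- For a run-in failure, adherence below 64% would by itself satisfy the requirement for a reason. SAP 6.2.1 tabulates discontinuation reasons for ITT subjects only, and SAP 5.2.1 excludes run-in failures from ITT.
- Protocol 8.3 iii refers PI review of recorded events back to 8.4, where the 90-day and 180-day timing stands.

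**Conclusion.** The point holds as a gap in scheduled assessment. Run-in failures are in the safety population but have no planned adverse event or device-deficiency review before they leave. Device-related event rates may be understated as a result, mainly for milder wear discomfort in subjects who stop wearing the belt.

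The size cannot be determined from the documents. With f from 5% to 30%, k from 0.5 to 3 and c from 0 to 1, relative understatement ranges from 0% to 56%. If 10% fail the run-in at the same risk as the rest, it is 10% with no capture and 5% with half captured. These figures assume that the event tables use the Safety Population, and they show what is possible rather than estimate what will happen. Serious events, falls and anything charted are much less exposed. This is an inexpensive improvement that should be made; it does not show that any stated figure is wrong.

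**What to change.** - In protocol 7.2 and 7.3, mark adverse events and device deficiencies at Visit 2 and at any withdrawal during the run-in. Include a brief direct question to, or check of, the subject or caregiver as well as the EMR review. An EMR review alone would repeat what 8.3 iii already requires and would miss uncharted discomfort.
- For each run-in failure, record why the belt was not worn, beyond the fact that adherence fell below 64%.
- Amend protocol 8.4 and reconcile it with SAP 5.2.4 and 8.1, so that the event window starts at belt assignment. Name the population for the event tables.
- Report adverse events of run-in failures separately in the safety tables.
- SAP section 9 shows that many belt subjects have already exited. For past run-in failures, a review of the EMR for days 0 to 14 is still feasible, though it can recover charted events only.

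The cost is a few minutes at a visit that already takes place, small CRF and wording changes, and possibly a slightly higher reported device-related event rate.
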